#### MTD Dose Adjustment Procedures.

Figure 2 (section 1.1) outlines the dosing approach. Dose adjustment procedures are outlined in section 6.3.

#### Side Effect Acceptability Ratings.

Our existing and previously tested **digital diary** will automate alerts for questions about side effects after infusion start at 15-, 30-, 60- minutes, and every 4 hours in the first 24 hours after infusion start (Figure 1, section 1.1). The diary has been tested and used by our group in previous work; alerts coincide with RASS assessments and similar timing of clinical assessments for routine CD nursing care and monitoring (i.e., is not more burdensome or intrusive to patients than routine clinical post-CD care). The digital diary will assess side effects

(i.e., dizziness, lightheadedness, bad dreams, nausea, vomiting, itchiness, and hallucinations: all dichotomous outcomes). Any positive response to any item will trigger the subject to rate their acceptability of side effects in the following way. Patient-reported acceptability is defined based on theoretical framework of acceptability and focused on constructs of *Burden* ("Would experiencing side effects keep you from participating in this intervention (ketamine) again?" yes/no) and *Affective Attitude* ("Based on your experience with this medication, would you be willing to participate in this intervention (ketamine) again?" yes/no). Either a negative response to Attitude, or a positive response to Burden, will define patient unacceptability.

#### Side Effects.

Monitoring during the infusion will follow our clinical standards of perioperative ketamine monitoring. A maternal side effect digital diary will also be used. The digital diary has been previously developed and tested in our preliminary lactation volunteer study. The diary alerts questions to patients include the Richmond agitation-sedation scale (RASS), dysphoria (LSD short form^105), and side effects. Automated alerts for abnormal responses go to clinical and research staff for immediate action. Any report of side effects will trigger a blood draw for analysis and correlation to measured plasma levels.

### Postpartum 12-week Follow-up Procedures.

Figure 1 (section 1.1) outlines weekly follow-up procedures. Participants will receive weekly surveys containing the questionnaires that are specified in Appendix 1. Surveys focus on pain and depression symptoms throughout the postpartum period.

# 7.1 Screening Procedures

Per our existing research procedures, patients will be screened from the Magee-Womens Hospital OB surgery schedule by dedicated trained research associates. Screening will be completed using the "Core Surgical PowerChart" and "Epic" Electronic Health Record (EHR) systems. All procedures will follow existing processes with clinicians for patient enrollment in research. Patients scheduled for CD are contacted prior to surgery by phone or in person to assess eligibility, explain the study protocol, and provide consent. Patients who are eligible within the prenatal clinics will be contacted prior to surgery in person, via a MyUPMC message or using videoconferencing to explain the study and obtain consent.

#### 7.2 Study Entry Procedures

Participants will be screened for eligibility prior to consent. Inclusion criteria and exclusion criteria are described in Sections 5.2 and 5.3.

# 7.3 Study Drug Administration

Following the cesarean delivery, the initial drug administration will be made after cord clamping and once anesthesiologist has declared hemodynamic stability (i.e., infusion starts approximately 5-15 minutes after delivery,  $\pm$  30 minutes). The infusion will be completely stopped at 12 hours after the start of infusion. The same infusion pump will follow the patient throughout the postoperative period for 12 hours until completion of the study drug. No manipulation of the infusion pump will occur by the

patient. Adjustments to the rate will be at the discretion of the study team and can be physically made by study personnel qualified and trained in these procedures, or by clinical care providers under direct orders from the study team.

### 7.4 Safety Assessments/Procedures During Treatment

Maternal monitoring during the infusion will follow our clinical standards perioperative ketamine monitoring and the standard Magee system safety precautions for administration of a controlled substance will be in place to protect from any misuse. A licensed and qualified anesthesia provider (resident, fellow, nurse anesthetists, or anesthesiologist) will be present during the first 30 minutes of the infusion and will have the option to treat blood pressures >180/100 mm Hg or heart rate >110 bpm. The study infusion will be discontinued if 3 consecutive measurements within a 15-minute interval remain above protocol-defined limits despite intervention (section 6.3). Maternal side effect symptomology monitoring will occur throughout the ketamine infusion. Automated alerts for maternal side effect responses go to clinical and research staff for immediate action. Any report of side effects will trigger a blood draw for analysis and correlation to measured plasma levels.

An independent DSMB will define frequency of monitoring of tolerability and DLT data. The severity of adverse events are classified in section 10.1

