# 1 Protocol Overview

Study Description	The purpose of this study is to identify a tolerable dose for postpartum ketamine infusion using a maximum tolerated dose (MTD) 3+3 design. A loading dose over 1 hour will be the MTD variable to be tested, as our data suggest that ketamine side effects occur with the loading dose.
Study Population:	Patients having cesarean delivery (CD) who are either: 1) planning not to breastfeed; or 2) are receiving ketamine as part of clinical care, will be enrolled. Ketamine will be started in postpartum patients, after cord clamping.
Planned Sample Size:	The projected sample size will be a maximum of 12 patients with complete primary outcome data within the MTD 3+3 design.
Participating Institutions (if a multicenter clinical trial)	N/A

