# 3.4 Endpoints

# 3.4.1 Primary Endpoint

Maximum Tolerated Dose (MTD). The MTD will be defined as the dose at which fewer than 33% of patients experience a DLT defined by intolerability.

Tolerability (dichotomous Yes/No)

Tolerability (YES) will be defined as: lack of adverse events (adverse event defined as: severe unresolved hemodynamic effect: systolic blood pressure <80 or >160, heart rate <40 or >120).

Lack of Tolerability will be defined as presence of any adverse event (i.e., severe unresolved hemodynamic effect: systolic blood pressure <80 or >160, heart rate <40 or >120).

A **DLT** event is defined by complete infusion cessation due to intolerable side effect acceptability ratings by patient, OR the experience of an intolerable event as defined above. The escalation of dosing will be as noted in Figure 2 and is based on a modified Fibonacci sequence  $^{101,102}$  with smaller proportional increases in dose in the escalation scheme. Escalations occur until 2 in a cohort of 3 to 6 experiences DLT (i.e., until  $\geq$ 33% of patients experience DLT at that dose). The dose **below** this level estimates the MTD.

Participants will be classified as having had a DLT if any of the following conditions are met:

- Persisting (i.e., unresolved after 3 consecutive measurements within a 15-minute interval)
  hemodynamic side effects defined as below and despite treatments or minimizing
  infusion rates as specified.
  - Systolic blood pressure <80 or >160
  - Heart rate <40 or >120
- Complete infusion cessation due to intolerable side effect acceptability ratings by patient

Primary Outcomes will be measured at a minimum of every 4-hours from the start of the ketamine infusion (t = 0) for 24-hours (12-hours post infusion cessation). Additional assessments will be administered between the 4-hour measurements if any adverse event or side effect is noted by the patient.

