# Events that Trigger Dose Adjustment Procedures:

- Persisting unresolved hemodynamic side effects defined as Systolic blood pressure <80 or >160,
   Heart rate <40 or >120^33
  - o Unresolved after 3 consecutive measurements within a 15-minute interval
- Persisting (i.e., unresolved within 1 hour of onset) side effects sedation, dizziness, lightheadedness, persistent itchiness, bad dreams, hallucinations, or other side effects that are reported as not acceptable to patients or clinicians, despite minimizing infusion rate.
- Table 1 includes procedures for dose adjustments.

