# Patient Reported Side Effects Dose Delays or Adjustments

[figure not shown]
- Side Effect Acceptability ratings are defined in section 3.4.2. Patient reported side effects (i.e., dizziness, lightheadedness, bad dreams, nausea, vomiting, itchiness, and hallucinations: all are dichotomous outcomes). These side effects will be evaluated based on patient-specific reports of how "acceptable" or "unacceptable." Patients reporting side effects and rating them as "unacceptable" will follow the dose delay or adjustment described in the Table 1. If side effects are rated "acceptable" then no dose delays or adjustments will occur.
- Figure 3 Decision Chart for Acceptability Based dose revisions.

Table 1. Loading and Maintenance Dose Adjustment Procedures:

Systolic blood pressure <80 or >160, Heart rate <40 or >120  Monitor for 5 minutes minutes for symptom resolution  Monitor for 5 minutes for symptom resolution  If event does not resolve  Hold infusion for 5 box (e.g., 0.05mg/kg/hr) and continue infusion.  If event does not resolve  Hold infusion for 5 box (e.g., 0.05mg/kg/hr) and continue infusion.  May D/C infusion and monitor subject for safety as	Event	1st Action	2 nd 1	Action	3rd /	Action	If event does not resolve
Pressure <80 or >160,   Heart rate <40 or >120   Heart rate <40 or >1							
monitor subject for safety as described in Section 7.4 and described in Section 7.4 and 7.5  Event qualifies as DLT	pressure <80 or >160,	labetalol or hydralazine per managing anesthesiologist Monitor for 5 minutes for symptom	for 5 minutes - symptom recheck at 5	(e.g., 0.05mg/kg/hr reduced to 0.025 mg/kg/hr) and continue	for 5 minutes - symptom recheck at 5 minutes:  May D/C infusion based on investigator discretion and monitor subject for safety as described in Section 7.4 and	(e.g., 0.025mg/kg/hr reduced to 0.013 mg/kg/hr) and continue	minutes of unresolved hemodynamic effect:  D/C infusion and monitor subject for safety as described in Section 7.4 and 7.5  Event qualifies

Event	1st Action	2 nd A	Action	3rd A	Action	If event does not resolve
		If event does not resolve	If the event resolves	If event does not resolve	If the event resolves	 1650.776

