### 9 Protection Against Risks

# 9.1 Management of drug related toxicity

The PI is a practicing, board-certified clinical anesthesiologist with extensive experience in the administration of this study drug under normal clinical circumstances. The study drug will be started during routine anesthesia care where monitoring is the strictest and closest, thereby enabling early detection of any safety events. The patients will remain monitored in an appropriate care environment throughout the duration of the 12-hour drug infusion, enabling timely detection and treatment of any serious events should they occur. Staff will also be trained to be familiar with common and uncommon side/adverse events for reporting.

Supportive care drugs that may be used in the event of drug related toxicity:

- Event: Persisting unresolved hemodynamic side effects defined as Systolic blood pressure <80 or >160, heart rate <40 or >120, unresolved after 3 consecutive measurements within a 15-minute interval
  - Supportive care medications:
  - Labetalol 10-20mg IVP or Hydralazine 10-25mg IVP p.r.n. hypertension at discretion of managing anesthesiologist.
- Event: Persisting side effects sedation, dizziness, lightheadedness, bad dreams, hallucinations, or other side effects that are reported as not acceptable to patient or clinicians, despite minimizing infusion rate
  - Supportive care medications:
  - o Midazolam 1-4mg IVP p.r.n. dysphoria, at discretion of managing anesthesiologist.

Refer to Section 6.8 for Rescue Drugs.

Refer to Section 6.3 of the protocol for instructions on dose delays and modifications.

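### Section 7.4's option to treat systolic pressure in the first 30 minutes (>180 mm Hg) sits 20 mm Hg above the >160 limit used in Table 1, the DLT definition and section 7.4's own stopping rule

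*Combined protocol and SAP*

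**What the plan says.** Section 7.4 covers safety procedures during treatment. It states that "A licensed and qualified anesthesia provider (resident, fellow, nurse anesthetists, or anesthesiologist) will be present during the first 30 minutes" of the infusion, and that this person "will have the option to treat blood pressures >180/100 mm Hg or heart rate >110 bpm". Its next sentence stops the infusion if three consecutive measurements within 15 minutes "remain above protocol-defined limits despite intervention (section 6.3").

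The limits in section 6.3 are different. Its list of dose-adjustment triggers begins with "Persisting unresolved hemodynamic side effects defined as Systolic blood pressure <80 or >160", together with heart rate below 40 or above 120. The hemodynamic row of Table 1 uses the same values, and its first action is "labetalol or hydralazine per managing anesthesiologist", followed by infusion holds and 50% rate reductions. Section 9.1 gives the supportive drugs for the same event: "Labetalol 10-20mg IVP or Hydralazine 10-25mg IVP p.r.n. hypertension at discretion of managing anesthesiologist".

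Section 3.4.1 counts a DLT for persisting "hemodynamic side effects defined as below and despite treatments or minimizing" of infusion rates, with the systolic upper limit again at 160. Section 12.3 repeats 160 in the tolerability definition used for the primary analysis.

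**The concern.** An option to treat is useful when it opens before, or at, the limit that defines the bad outcome. For systolic pressure in section 7.4 it opens after that limit. A reading between 161 and 180 in the attended period is an event under Table 1 but lies below the figure that section 7.4 gives the person at the bedside.

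These readings matter because they feed the primary endpoint. Both the DLT definition and the section 7.4 stopping rule assume that treatment or another intervention has been tried. Two figures for when to try it invite different handling of similar patients: one provider may give an antihypertensive under Table 1, and another may take 180 as the point to act.

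The timing adds weight. The Protocol Overview says "A loading dose over 1 hour will be the MTD variable to be tested, as our data suggest that ketamine side effects occur" at that stage, and the attended period falls inside the loading hour. Under section 3.4.1, two DLTs in a cohort of three to six patients stop escalation, so the handling of a single patient can count.

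**Working it through.** No power or sample-size figure is involved. The check sets the current thresholds side by side and subtracts.

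| Place | What it governs | Systolic upper value (mm Hg) | Persistence required |
|---|---|---|---|
| 7.4, provider present | Option to treat, first 30 minutes | 180 (with diastolic 100) | None stated |
| Table 1 (6.3), hemodynamic row | Drug as first action, then holds and reductions | 160 | None in the event column |
| 6.3, trigger list | Dose adjustment | 160 | 3 consecutive readings in 15 minutes |
| 9.1 | Supportive drugs | 160 | 3 consecutive readings in 15 minutes |
| 7.4, stopping rule | Stopping the infusion | 160, through 6.3 | 3 consecutive readings in 15 minutes |
| 3.4.1 | DLT | 160 | 3 consecutive readings in 15 minutes |

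**Which comparison is direct.** Sections 3.4.1 and 12.3 define an endpoint, not a treatment point, and the triggers in 6.3 and 9.1 require persistence. Only the Table 1 row, like section 7.4, ties drug treatment to a pressure value without a persistence condition. The direct clash over treatment is therefore between section 7.4 and that row. The other places show which limit the treatment option ought to precede.

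**Systolic gap.** 180 − 160 = 20 mm Hg. The option opens above the limit.

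**Heart rate, as a contrast within the same sentence.** The option is >110 and the limit is >120: 120 − 110 = 10 bpm. The option opens below the limit. Only the systolic order is reversed.

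**Diastolic.** The value of 100 has no counterpart in the DLT definition or in Table 1, so no comparison is possible.

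**Period affected.** 30 / 60 minutes = 50% of the loading hour, and 30 / (12 × 60) = 30 / 720 = 4.2% of the infusion. Of the three scheduled assessments in the loading hour (15, 30 and 60 minutes), two fall in the attended period.

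**What happens to a reading of 161–180 in that period.** Under Table 1 it is an event with a drug option, then holds and reductions. Under section 7.4 it is below the stated option. If three consecutive readings within 15 minutes stay there despite intervention, the same section stops the infusion.

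**Effect on the MTD.** The documents give no frequency for systolic readings of 161–180, so there is no input from which to calculate a change in the DLT count.

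**The case against.** The best defence is that the text already copes. Section 7.4 grants an option and forbids nothing, its next sentence sends the reader to section 6.3, and Table 1 there offers labetalol or hydralazine above 160. This stands in full as an answer to one stronger reading, that patients at 161–180 may not be treated. The documents do not say that.

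A second defence concerns the endpoint. A DLT counts only after the specified treatments or rate reductions, and Table 1 is where these are specified. A provider who relied on section 7.4 alone would be departing from Table 1. This also stands. A reader might infer that untreated DLTs will follow, or that the MTD will be biased. The documents do not support that, because the holds and reductions still apply and no frequency is given.

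Two further inferences are tempting. One is that the conflict comes from split roles, because section 7.4 names several kinds of provider while Table 1 and 9.1 name the managing anesthesiologist. Nothing in the documents shows that the person present acts independently of that anesthesiologist. The other is that section 7.4 was overlooked when version 7.0 lowered the cutoff from 190 to 160. The version history does not list section 7.4 for that change, but it does not say why, and the point does not need the explanation.

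Finally, the version history mentions a manual (MOP) that is not among the documents. It may settle bedside practice, so inconsistent handling is a risk and not an observed fact.

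None of this removes the two figures. A safety section that names a pressure tells staff when to act, even if the wording is permissive, and the figure it names is on the wrong side of the limit.

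**Conclusion.** The point holds as an inconsistency in a safety threshold within the current text. The systolic option in section 7.4 is 20 mm Hg above the value at which Table 1 begins drug treatment, and above the limit at which a persisting event becomes a DLT and ends the infusion. The heart-rate option in the same sentence is ordered correctly. The conflict covers readings of 161–180 during the first half of the loading hour.

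The consequence is limited to conflicting bedside guidance on readings that feed the primary endpoint. Its effect on the DLT count and the MTD cannot be quantified. The conclusion rests on two readings of the text: that the first number in the section 7.4 pair is a systolic treatment value, and that the hemodynamic row of Table 1 attaches its first action to systolic pressure above 160 as listed. The textual mismatch is certain. How often it would change care is unknown. It should be corrected, because the correction is cheap and the version history attributes the 160 limit to a DSMB recommendation.

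**What to change.** In section 7.4 change the systolic value from 180 to 160 and refer to Table 1. For example: *the provider may treat systolic blood pressure >160 mm Hg, as set out in Table 1 (section 6.3), or heart rate >110 bpm*. This leaves the option permissive, leaves the heart-rate value alone and makes Table 1 the single source for the sequence of actions.

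The diastolic value needs a separate decision. The protocol does not say whether both numbers of the 180/100 pair must be exceeded or either one, and Table 1 has no diastolic action. The sponsor should state whether diastolic >100 mm Hg is kept as an option in its own right.

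The cost is one wording amendment, with prospective IRB approval under section 14.1, and brief staff retraining. Sample size and analysis do not change.

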### 7.5 Safety Assessments/Procedures After Ketamine Infusion Stop

Maternal side effect monitoring following the infusion will continue at 4-hour intervals for 12-hours after the cessation of ketamine infusion. Monitoring will occur via clinical staff monitoring and via patient self-report indices of side effect symptomology (Figure 1; section 1.1).

After the study drug infusion is complete, safety and efficacy assessments consist of the following. Digital diaries will assess self-reported side effects according to the study schematic Figure 1; 1.1, until 12 hours after infusion discontinuation. Vital signs will be monitored during that same period.

#### 7.6 Safety Assessments/Procedures During Postpartum Surveys

Efficacy assessments, exploratory in nature, will consist of pain and depression symptom screening at regular intervals from one week postpartum until 12 weeks after delivery, according to the time intervals indicated in the study schematic Figure 1; 1.1. Positive screens for depression will be initiate an immediate response to the study team. The protocol for positive depression screens is presented in Appendix 4. All patients who screen positive for depression (EPDS total score > 14 or positive answer to question #10) will be contacted and receive consultation instructions.

After all study procedures are complete 12 weeks after delivery, there will be no further active assessments of safety and efficacy by study staff. Participants will continue to have access to their primary care physicians and emergency services.

#### 8 Potential Risks and Benefits

# 8.1 Reasonably Foreseeable Risks Related to Study Drug

Common side effects of ketamine are sedation, dizziness, lightheadedness, bad dreams, hallucinations, euphoria, dysphoria, nausea, vomiting. These risks are minimized by using doses below the doses that we typically see these side effects. Seriousness: mild to moderate.

Uncommon effects of ketamine include hypertension or hypotension, tachycardia, or bradycardia. These risks are minimized as much as possible by using doses below the doses that we typically see these effects. If these effects are noted, the drug will be stopped until the effects dissipate. Should the effects not dissipate, the PI will evaluate and determine whether the patient requires additional care. If these uncommon effects are experienced, an SAE log will be completed and the IDSMB and IRB notified. Seriousness: mild to moderate

# 8.2 Reasonably Foreseeable Risks Related to Research Interventions

Risks to confidentiality. There is a risk of breach of confidentiality with the screening procedures and the collection and storage of personal health information. To protect against this risk, all screening procedures will be done by study staff who have been completely trained in HIPAA/privacy procedures; all data collected will be identifiable only by a unique subject ID number, and no personal identifiers will be stored with the data. Linkage files identifying subjects will be stored only in physical records that are kept in locked files accessible only by study staff; electronic data will be handled and protected whereby any linkages between study ID number and patient identification will be separated, password protected, and stored behind the UPMC firewall. There are some cases in which a researcher is obligated or authorized by law to report mental health symptoms, such as serious threats to public health and safety. For example, if patients indicate that they are in imminent risk of harm (e.g., suicide or serious threats toward the wellbeing of others), the researchers will contact the appropriate authorities to protect patients or the public. Seriousness: mild

*Risks of inconvenience from surveys.* To minimize the inconvenience/time burden on participants associated with the survey questions, we will use an electronic (email) interface preferentially and will minimize the number of questions to strictly only the number necessary to address important aspects of our study questions. Seriousness: mild

*Risk of survey discomfort.* An uncommon risk includes inconvenience and potential emotional discomfort are risks associated with answering survey questions. Subjects will be asked to answer questions regarding pain and depression before, during, and after having their babies. Answering these questions may be viewed as an inconvenience. Seriousness: mild

*Risks of IV blood collection.* Common risks associated with blood collection include bruising or swelling at the collection sight, discomfort during venous blood draw, and infection. Seriousness: mild

Risk of sub-anesthetic ketamine infusion dose titration. Common risks include nausea, euphoria, dizziness, or lightheadedness. Seriousness: mild. Uncommon risks include temporary hypertensive event.

Seriousness: mild to moderate; uncommon risks include hallucinations or dysphoria. Seriousness: mild to moderate.

